6.8 Rescue Therapy

Topical ocular steroids will be considered Rescue Therapy.

In the event of worsening of signs or symptoms that, in the clinician's opinion is so severe as to necessitate a change of medication, ciclosporin and/or antihistamines may be introduced or increased in dose/frequency and this will be considered as a treatment failure for purposes of efficacy analysis.

The introduction or increase in dose/frequency of ciclosporin or antihistamines will be considered as Rescue Therapy.

After entry into the trial, subjects will be recommended to not receive Rescue Therapy from the first dose of rVA576 as far as possible unless assessed by PI as needed.

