| 10 | . Corneal perforation |
| | . Uncontrolled glaucoma (increase in dose of glaucoma |
| | medication or surgical intervention for glaucoma within 3 |
| | months prior to entry) |
| 12 | . Pregnancy (females) |
| | . Breast feeding (females) |
| | . Known allergy to ticks or severe reaction to arthropod venom |
| | (e.g. bee or wasp venom) |
| 15 | . Use of topical ocular steroids within 7 days of the Screening |
| | visit |
| 16 | . Failure to satisfy the PI of suitability to participate for any |
| | other reason |

| Treatment Regimen: | Part 1: Sterile eye drops 0.25% w/v (2.5 mg/mL), solution in 6mL glass vials containing 1mL solution. Eye dropper pipettes will also be supplied. |
|---------------------------|--|
| | Part 2: Sterile rVA576 0.25% w/v (2.5 mg/mL) or placebo solution in 6 mL glass vials containing 1 mL. Eye dropper pipettes will also be supplied. |
| | The product should be administered as one drop to each eye every 12 hours (i.e. twice daily) for a total of 56 Days. |
| | Background therapy: Patients should continue on whatever topical therapy they are on at the time of screening (ciclosporin or antihistamines) but this should remain stable during the trial. Lubricants and artificial tears may be used ad libitum but should not be administered for 15 minutes before or after the trial medication. In the event of worsening of signs or symptoms that, in the clinician's opinion is so severe as to necessitate a change of medication, ciclosporin and/or antihistamines may be introduced or increased in dose/frequency and this will be considered as a treatment failure for purposes of efficacy analysis. Topical corticosteroids may be added following introduction or increase in ciclosporin/antihistamine therapy if considered necessary. |
| | Should not be on topical ocular steroids at start of the trial but may be used as rescue therapy during the trial if necessary (see above) |
| Duration of Treatment: | 56 Days each for active and placebo dosing plus 7 (± 2) days between screening and entry and 28 (± 2) days between final trial visit and follow up visit. Total trial duration 6-12 months. |

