6.3 Dosing Scheme

Part 1: The product will be supplied as a sterile 0.25% solution in 6 mL glass vials containing 1 mL of rVA576 solution. Single use eye dropper pipettes will also be supplied. The vials are for single use (one drop to each eye) and must be retained and returned to the site at each clinic visit.

Part 2: The product will be supplied as a sterile 0.25% solution in 6 mL glass vials containing 1 mL of solution of either rVA576 or placebo. Eye dropper pipettes will also be supplied. The vials are for single use (one drop to each eye) and must be retained and returned to the site at each clinical visit.

The patients will be randomised to receive either rVA576 active or placebo in double masked fashion. The product should be administered as one drop to each eye every 12 hours (i.e. twice daily) for a total of 56 days.

The product should be stored frozen in the site Pharmacy until the first 7 days' supply is to be given to the patient and then every 7 days thereafter. The product once unfrozen should be kept at 2 - 8 °C for a maximum of 7 days.

All patients entering the trial will have been on maximal topical therapy (meaning the maximal labelled dose or frequency of dosing) for at least three months before entry on the study and will continue on this therapy (background therapy) for the duration of the study.

Background therapy:

Patients should continue on whatever topical therapy they are on at the time of screening but this should remain stable during the trial. Lubricants and artificial tears may be used *ad libitum* but should not be administered for 15 minutes before or after the trial medication. In the event of worsening of signs or symptoms that, in the clinician's opinion is so severe as to necessitate a change of medication, ciclosporin and/or antihistamines may be introduced or increased in dose/frequency and this will be considered as a treatment failure for purposes of efficacy analysis. Topical corticosteroids may be added following introduction or increase in ciclosporin/antihistamine therapy if considered necessary.

See Concomitant Medications for further details of choice of eye lubricants.

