Patients should not have used topical ocular steroids for 7 days prior to entry to the trial but, at the discretion of the investigator, may receive them as rescue medication during the trial. A comparison of the number of patients requiring rescue therapy at any stage of the trial and the number on such therapy at the end of the trial will be an additional exploratory endpoint.

Use of systemic immunosuppressives, antihistamines or corticosteroids during the trial is forbidden. Patients who, in the opinion of the investigator, require such treatment will be withdrawn from the trial. If the reason for giving such treatment is related to their primary pathology (AKC, VKC, or severe allergic conjunctivitis (SAC or PAC)) they will be regarded as treatment failures.

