6.10.2.3.2 Analysis

Change from baseline (Day 1) for the total score at Day 14, Day 28, Day 42 and Day 56 will be analysed using a mixed-effect model for repeated measures. The model will include baseline total clinical score as a covariate, treatment group, visit and patient group (AKC/VKC or SAC/PAC) as fixed factors and the treatment arm by visit interaction.

The variance/covariance matrix structure that results in best model fit will be selected using the process described in section 6.10.2.1.2.

Assumptions of normality will be assessed visually using diagnostic plots. Should assumptions of normality not hold, transformations such as percentage change and ratio to baseline will be considered. If there remains uncertainty regarding the assumptions an alternative analysis, for example non-parametric analysis, may be considered.

The LS means and 95% confidence interval will be presented for each visit and treatment. The adjusted LS mean difference (nomacopan - placebo) and 95% confidence interval will be presented for each visit.

A null hypothesis of no change in clinical score at Day 56 between treatment groups (nomacopan - placebo) will be assessed and a p-value will also be reported based on the relevant mixed-effect model.

Where there is sufficient data (see section 6.2) the item scores will be analysed using the same method as for the total score.

Where there is a sufficient number of patients receiving rescue therapy, additional analysis (as described above) may be conducted using the same methods as the recorded clinical scores by imputing the worst-case score for all post-rescue therapy visits.

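### The protocol's treatment-failure event does not match its rescue event, and the SAP has no rule that carries treatment failure into the efficacy analysis

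*Protocol*

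**What the plan says.** **Failure.** The protocol gives two triggers.

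- The synopsis, 6.3 and 6.8 all state that, when worsening is so severe that treatment has to be altered, "ciclosporin and/or antihistamines may be introduced or increased in dose/frequency and this will be considered as a treatment failure for purposes of efficacy analysis".
- Section 6.3 also covers patients who need systemic immunosuppressives, antihistamines or corticosteroids. They are withdrawn, and if the reason is their primary eye disease, "they will be regarded as treatment failures".

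**Rescue.** Protocol 6.8 also names two components: "Topical ocular steroids will be considered Rescue Therapy" and "The introduction or increase in dose/frequency of ciclosporin or antihistamines will be considered as Rescue Therapy". The failure label is attached to the second component and not to the first.

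**When ocular steroids may be given.** The wordings differ.

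- One paragraph of 6.3 says: "Topical corticosteroids may be added following introduction or increase in ciclosporin/antihistamine therapy if considered necessary". The synopsis has the same sentence, and then says that ocular steroids "may be used as rescue therapy during the trial if necessary (see above", which points back to it.
- A later paragraph of 6.3 says that patients, "at the discretion of the investigator, may receive them as rescue medication during the trial", and mentions no earlier step. Section 6.8 lists steroids as rescue without giving an order.

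**SAP.** The main analysis of the clinical score (6.10.2.3.2) is a repeated-measures model on change from baseline, with no term, exclusion or censoring for rescue or failure. If enough patients are rescued, an additional analysis may be done by "imputing the worst-case score for all post-rescue therapy visits". The SAP does not say how many patients are enough or what the worst-case score is. Rescue use is tabulated in 6.10.3.3. The term treatment failure does not appear in the SAP.

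**The concern.** The protocol announces a rule for the efficacy analysis: certain patients count as failures. Two things undermine it.

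First, the failure event and the rescue event are different sets. If an investigator relies on the discretionary wording and gives ocular steroid without a prior step-up, the patient is rescued but is not defined as a failure. A patient whose antihistamine alone is increased for severe worsening is a failure.

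Second, the SAP does not carry out the rule. Its nearest substitute is optional and follows rescue rather than failure, so it leaves out the systemic-treatment failures.

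At stake are a failure count that depends on which paragraph is followed, and a stated efficacy rule that no planned analysis applies. The composite score is the measure by which Protocol 5.1 defines efficacy.

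**Working it through.** The documents give no figure to reproduce, so the check sets the texts side by side. Each row is a possible course for a Part 2 patient.

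| Course | Failure (Protocol synopsis, 6.3, 6.8) | Rescue (Protocol 6.8) | SAP main model | SAP worst-case analysis |
|---|---|---|---|---|
| Ciclosporin/antihistamine introduced or increased for severe worsening | Yes | Yes | Recorded scores | Covered, if run |
| Ocular steroid after such a step-up | Yes, from the step-up | Yes | Recorded scores | Covered, if run |
| Ocular steroid with no prior step-up | No | Yes | Recorded scores | Covered, if run |
| Systemic treatment for the primary eye disease | Yes, and withdrawn | No | Recorded scores up to withdrawal | Not covered |

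Four things follow.

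1. Failure and rescue disagree in rows 3 and 4, in opposite directions. Neither set contains the other.
2. Row 3 can occur only if the discretionary wording allows steroid without a step-up. Under the stepwise wording every steroid-rescued patient falls in row 2.
3. The main-model column is the same for everyone. Changing the failure label alone changes no estimate in the SAP.
4. In row 4, visits after withdrawal are missing, and SAP 6.2 imputes no missing data. The systemic failures therefore get no failure handling in either analysis.

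SAP 6.17 lists three changes from the protocol: the baseline definition, the comfort-score interval and the Safety Analysis Set. The unimplemented failure rule is not among them.

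**Scale of one patient in the failure count.** Protocol 6.7 randomises 16 patients 1:1, so a full arm has 16/2 = 8. Reclassifying one patient moves that arm's failure proportion by 1/8 = 12.5 percentage points. The number of row 3 patients is not given; it could be anywhere from 0 to 8 per arm.

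**Scale of one patient in a worst-case analysis (illustration only).** Replacing a recorded score s by the scale maximum M moves the raw mean of an arm of 8 at that visit by (M − s)/8. Assume that s equals the entry threshold:

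- AKC/VKC: (33 − 18)/8 = 1.875 points
- SAC/PAC: (27 − 15)/8 = 1.5 points

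Over all possible s the range is 0 to 33/8 = 4.125 points, or 0 to 27/8 = 3.375 points. These are raw-mean shifts, not model estimates. They show what depends on whether the optional analysis is run and whom it covers.

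**The case against.** The case on the other side is substantial, and much of it stands.

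- **Order of steroid use.** Neither 6.8 nor the discretionary sentence in 6.3 says outright that steroid may come first; they are silent on order. The synopsis and the other paragraph of 6.3 are stepwise. Read that way, every steroid-rescued patient has already failed. This stands, so row 3 is conditional on an ambiguity. The systemic mismatch and the missing SAP rule do not depend on it.
- **Failure triggers.** A reader of 6.8 alone might infer that a topical step-up is the only route to failure. Section 6.3 contradicts this with the systemic trigger.
- **Conflict between documents.** A reader might infer that a steroid-first patient is a failure under the SAP and a non-failure under the protocol. The SAP classifies nobody as a failure, and its optional analysis already includes steroid rescue because 6.8 defines it as rescue.
- **Effect on the main result.** A reader might infer that failure status decides whether post-rescue scores count towards the drug effect, or that the mismatch moves the treatment difference by several points. The main model ignores failure status. A shift of that kind is the gap between recorded scores and worst-case imputation, and it arises for any rescued patient, including one with only an antihistamine increase. Nor do the documents say which arm would be rescued more often, so no direction of bias can be claimed.
- **Weight.** The primary endpoint is safety, the sample size was chosen on practical grounds, and Protocol 11.5 treats efficacy significance as nominal. Rescue is already tabulated by arm and interval. This limits the severity but does not supply the missing rule.

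**Conclusion.** The point holds in a limited form. Failure and rescue are different events in the protocol, no current text makes topical ocular steroid use by itself a failure, and the SAP neither implements the failure rule nor records that it has been dropped. The optional worst-case analysis is only a partial substitute, because it may not be run and it omits the systemic trigger.

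The steroid part assumes that ocular steroid can be given without a prior step-up, which the protocol leaves unresolved. The effect on the treatment difference is unknown, because the documents give no rescue rate, SD or effect size. The one firm figure is 12.5 percentage points in an arm's failure proportion per reclassified patient, assuming 8 per arm.

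This should be corrected, but it does not threaten the primary safety analysis.

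**What to change.** 1. **One analysis event.** In the synopsis, 6.3, 6.8 and SAP 6.10.2.3.2, define treatment failure for the efficacy analysis as either any Rescue Therapy listed in 6.8, including topical ocular steroid, or the systemic-treatment trigger in 6.3, counted from its start date. This concerns analysis only and changes no rule about who may receive what.
2. **An analysis that uses it.** Make the SAP worst-case analysis after that event a planned one. State that the worst case is the indication's own maximum (33 for AKC/VKC, 27 for SAC/PAC) and that it also fills scheduled visits after a systemic-treatment withdrawal, as an exception to SAP 6.2. Without this step the new definition alters no result.
3. **Record of change.** Until the texts agree, list the difference in SAP 6.17.
4. **Separately,** reconcile the synopsis and the stepwise paragraph of 6.3 with the discretionary paragraph of 6.3 and with 6.8 on the order of steroid rescue. This review does not say which is right.

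The cost is a few sentences in the protocol and a short paragraph in the SAP, settled before unmasking, by which point Protocol 11.1 requires the SAP to be final. The downside is small: the failure count may rise, and one more analysis is reported.

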4.1 Inclusion Criteria

- 1. Aged 18 and above
- 2. Diagnosis of moderate to severe AKC,VKC or severe allergic conjunctivitis (seasonal or perennial). Defined as:
 - AKC, VKC a composite symptom/sign score from one eye of ≥ 18 out of 33 (see Clinical Scoring 17.1)
 - Severe allergic conjunctivitis a composite symptom/sign score from one eye of \geq 15 out of 27 (see Clinical Scoring Section 17.1)
- 3. Will have had received some topical therapy during the last 3 months without improvement but will not currently be receiving systemic immunotherapy. Topical therapy may be topical calcineurin inhibitors, antihistamines or corticosteroids alone or in combination. Lubricants or artificial tears will not a count as topical therapy for these purposes.
- 4. Will have had at least 7 days without topical ocular corticosteroids prior to entry
- 5. Willing to give informed consent
- 6. Willing to use highly effective contraceptive precautions for the duration of the study and for 90 days after the last dose of IMP.
- 7. Willing to avoid prohibited medications for duration of study (see list of prohibited medications)

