6.10.3.3 Rescue therapy

The number and percentage of patients that received a rescue medication (as indicated on the Concomitant Medications CRF page) at any stage of the trial (during Day 1 to Day 56 (last dose) and during Day 56 to Day 84 (follow-up visit) to be presented separately) and the number and percentage of patients that were receiving a rescue medication at the end of the trial (indicated as ongoing on the CRF) will be presented in a summary table by treatment group.

The number and percentage of patients that received a rescue medication will be presented for each treatment group for Days 1 to 14, Days 15 to 28, Days 29 to 42 and Days 43 to 56 to compliment the intervals for the efficacy analysis. The percentage will be out of the number of patients at each timepoint who had data for comfort scores to be calculated.

A patient is considered to have taken rescue medication during an interval where the start date (Day 1 or later) occurs during that interval, or if they continue to receive rescue medication that started in a previous interval.

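### The rescue and topical treatment-failure rules still name ciclosporin although any topical calcineurin inhibitor is now permitted, so a tacrolimus step-up for worsening has no defined classification

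*Protocol*

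**What the plan says.** **Who may enter.** Protocol 4.1, criterion 3: "Topical therapy may be topical calcineurin inhibitors, antihistamines or corticosteroids alone or in combination". The Amendment 7 justification gives the reason: UK patients on this class almost all receive ciclosporin, while topical tacrolimus is more usual at the Spanish sites. That change lists only the synopsis and Section 4.1, criterion 3, as the places altered.

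**Background therapy.** Protocol 6.3 keeps patients on their topical treatment at screening, unchanged, and names no drug. The synopsis version of that sentence is narrower: "whatever topical therapy they are on at the time of screening (ciclosporin or antihistamines".

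**Rescue.** Protocol 6.8 has two triggers: "Topical ocular steroids will be considered Rescue Therapy" and "The introduction or increase in dose/frequency of ciclosporin or antihistamines will be considered as Rescue Therapy".

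**Treatment failure, topical route.** For worsening severe enough to need a change of medication, Protocol 6.3 says "ciclosporin and/or antihistamines may be introduced or increased in dose/frequency and this will be considered as a treatment failure for purposes of efficacy analysis". The synopsis and 6.8 carry the same rule.

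**Treatment failure, systemic route.** Protocol 6.3 also says "Use of systemic immunosuppressives, antihistamines or corticosteroids during the trial is forbidden". Patients who need such treatment are withdrawn, and if the reason is their eye disease, "they will be regarded as treatment failures".

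**Analysis.** SAP 6.10.3.3 reports "The number and percentage of patients that received a rescue medication (as indicated on the Concomitant Medications CRF page"), by arm and by two-week interval. SAP 6.10.2.3.2 allows, if enough patients are rescued, an additional analysis that gives a worst-case clinical score to every visit after rescue. The SAP lists no rescue drugs and defines no treatment-failure variable.

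**The concern.** The permitted class was widened, but the rules that classify a change within that class were not. Two patients may worsen equally and have their background calcineurin inhibitor increased equally. The one on ciclosporin meets both the rescue and the treatment-failure definitions. The one on tacrolimus meets neither.

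Two outputs depend on that status: the rescue comparison, which is an exploratory endpoint (Protocol 5.2.3), and the optional worst-case analysis of the composite score. With no written rule for tacrolimus, what reaches the CRF depends on how each site understands the word rescue, and sites in two countries may understand it differently. In a trial of this size, one patient counted either way visibly changes an arm's percentage.

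**Working it through.** The plan has no figure to reproduce: the sample size was set on practical grounds, and no rescue rate is assumed. The check is a comparison of rules, followed by arithmetic for scale.

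**Step 1. Test each rule against a topical tacrolimus start or increase for worsening.**

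| Rule | Drugs covered | Tacrolimus step-up |
|---|---|---|
| Criterion 3 (Protocol 4.1) | any topical calcineurin inhibitor, antihistamine or corticosteroid | tacrolimus user admitted |
| Background therapy (Protocol 6.3) | any topical therapy at screening, kept stable | departs from stability |
| Rescue (Protocol 6.8) | ocular steroids; ciclosporin or antihistamine started or increased | not met |
| Topical failure (synopsis, 6.3, 6.8) | ciclosporin and/or antihistamine started or increased | not met |
| Systemic failure (Protocol 6.3) | systemic immunosuppressive, antihistamine or corticosteroid | not met (topical drug) |
| Rescue count (SAP 6.10.3.3) | CRF indication, no list | undetermined |

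Tacrolimus is named only in the Amendment 7 justification. I found no rule elsewhere in either document that closes the gap.

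**Step 2. Weight of one patient in the rescue summary.** Part 2 has up to 16 patients randomised 1:1, so 16/2 = 8 per arm at full enrolment. One patient is 1/8 = 12.5 percentage points, and *k* unflagged step-ups in one arm are *k*/8. The documents do not give the number of tacrolimus users. Assuming 0 to 4 users per arm, the outer limit is 0/8 = 0 to 4/8 = 50 points. The upper end would need all four to be stepped up, left unflagged, and given no other listed rescue drug.

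**Step 3. Weight of one patient in the optional worst-case analysis.** Assume that worst case means the scale maximum (the SAP does not say) and that the observed score equals the entry threshold. One missed imputation then shifts the raw arm mean at that visit by (maximum − observed)/8:

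- AKC/VKC: (33 − 18)/8 = 15/8 = 1.9 points
- SAC/PAC: (27 − 15)/8 = 12/8 = 1.5 points

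For an AKC/VKC patient with an observed score of 10, the shift is (33 − 10)/8 = 2.9 points; with 25, it is (33 − 25)/8 = 1.0 point. These are raw means, for scale only. The model-adjusted means would differ.

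**The case against.** The case on the other side limits the consequences but leaves the mismatch in place.

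- **The CRF may catch it.** The SAP reads rescue from the CRF, whose completion instructions are not in the documents. A site could mark a tacrolimus step-up as rescue. This stands: the supportable claim is that such a patient may be missed or handled inconsistently. A reader might infer that the patient is certain to go uncounted; the documents do not show that.
- **The event leaves a trace.** It departs from stable background therapy. Deviations are listed under SAP 6.6, and background therapy and medications under SAP 6.8. This stands, but a listing does not enter the rescue percentage.
- **The main efficacy analysis does not use rescue status.** A reader might infer that scores improved by extra tacrolimus bias the composite-score model. That model (SAP 6.10.2.3.2) uses recorded scores for every patient, including those whose ciclosporin was increased, so reclassifying the event would not change its result. This stands in full.
- **The output affected is minor.** The rescue endpoint is exploratory and summarised without a test, and the imputation is conditional. This stands and limits the weight of the point.
- **It is not a country rule.** Classification follows the drug, and Amendment 7 calls tacrolimus more usual in Spain, not universal. Nor does unstratified randomisation imply systematic bias: an uneven spread of tacrolimus users between masked arms would be chance. Both stand.
- **Other triggers remain.** A tacrolimus user who also receives ocular steroids, or whose antihistamine is started or increased, still meets the rescue definition. This stands. No passage expressly says, however, that ocular steroids alone make a patient a treatment failure.

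**Conclusion.** The inconsistency holds. Following the protocol to the letter, a start or increase of a permitted topical calcineurin inhibitor other than ciclosporin for worsening is neither rescue nor treatment failure. It looks like an amendment that was not carried through: nothing in the documents gives a reason for separating two drugs of one permitted class.

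The effect is confined to the exploratory rescue summary and, if it is run, the worst-case analysis. Each misclassified patient is worth 12.5 percentage points in a full arm of 8 and, under the assumptions in step 3, about 1.0 to 2.9 points of an arm's mean composite score at a visit in the worst-case analysis. How many patients are involved is unknown and could be none.

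The primary safety endpoint and the main composite-score model are unaffected. Nor can a treatment-failure rate in the planned tables be distorted, since the SAP tabulates none.

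**What to change.** 1. Reconcile the synopsis, Protocol 6.3 and Protocol 6.8 with criterion 3 and the Amendment 7 rationale.
2. Add one sentence on classification for analysis, kept apart from the sentence on what may be given: for analysis, a start or increase of any permitted topical calcineurin inhibitor because of worsening is classified as the same change in ciclosporin would be. Simply exchanging the drug name in the failure sentence would not do, because that sentence also states what may be introduced, so the exchange would alter a clinical permission. Which changes of therapy are allowed is for the sponsor and investigators to reconcile.
3. Refer to that definition in SAP 6.10.3.3 and in the worst-case analysis of SAP 6.10.2.3.2, and in the completion instruction for the CRF rescue flag.
4. Check the flags of patients already enrolled against it before unmasking.

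The cost is a few sentences in the protocol and SAP, one CRF instruction, and a review of at most 16 Part 2 records, plus the 3 in Part 1 for consistent listings. The downside is that a few more patients may be counted as rescued.
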